- b. Feasibility: Number of patients who initiate Relief or UC/RMH [referral (based on clinical indication) for mental health care] and research procedures (timely referrals, assessments);
- c. Acceptability: Patient's treatment satisfaction at 6, 9, and 12 weeks.

Benchmarks of the study progress: Feasibility: At least 75% of Relief participants will complete Relief. Acceptability: We will obtain treatment satisfaction score at the end of Relief treatment.

- 4. Preliminary Effectiveness: Over the course of 12 weeks, Relief participants, compared to participants in UC/RMH [referral (based on clinical indication) for mental health care], will have greater (effect size) and clinically significant reductions in depression, pain-related disability.
- 5. Preliminary Evidence of Target Engagement/Secondary: The differential effect of Relief vs. UC/RMH in reducing depression and pain-related disability will be independently mediated by reduction of interoceptive focus and positive and negative emotions.

OVERVIEW OF DESIGN

Figure 1.

PROTOCOL

1. Study staff reviews the Electronic Health Records (EHR) on Electronic Privacy Information Center (EPIC) and will identify patients with diagnoses of chronic pain, a DSM 5 diagnoses of depression and anxiety, as well as patients who are on psychotropic and/or pain medications.
2. Study staff will also attend meetings at each of the PCP practices every few months to present/review the study and ask the PCPs to write down the names of any patients they think may be appropriate.
3. Study staff will then contact potential participants via phone. If they meet preliminary eligibility criteria (based on administering the phone screen script) and are interested, they will be invited to come to our offices in White Plains or NYC, or to schedule a video or phone appointment, depending on the circumstances. During the appointment, the consenting process will take place first, and then if the patient consents, the research assistant will conduct the screening assessment (either in person or remotely).
4. RA will then discuss the results of the assessment with [name].
5. If the patient is eligible, the RA will email the data manager with the patient information.
6. The data manager will randomize the patient to either Relief or UC/RMH.
7. The data manager will notify [name] and the supervising therapist (not administering the intervention) about the randomization.

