8. The supervising therapist will contact the physician to let them know that the patient is part of the study and whether they are receiving Relief or UC/RMH.
9. The supervising therapist will notify the patient that they are receiving Relief or UC/RMH and will assign a therapist to the patient if randomized to Relief.
10. Both groups will receive (from the RA or via mail):
 - Educational (TCAP) booklet
 - Withings Watch with charger
 - iPhone 7 with charger (if patient does not have a smartphone or doesn't want to use their own)
 - W2H application downloaded to smartphone
 - Technology Manual

In addition, patients randomized to Relief will receive a therapy participant guide from the study therapist.

11. Team weekly meetings:
 - Review recruitment (specifically the numbers of positive screen patients)
 - Referrals
 - Tracking of all patients; we will discuss:
 - The status of assessments
 - If in Relief, the status of therapy sessions
 - RAs will leave the room to protect randomization.
 - The data manager will generate charts with recruitment progress.

12. The RA will conduct assessments at follow up time points: 6, 9, and 12 weeks after the baseline assessment. The patient will receive \$25 (cash, check or gift card) for each assessment.
13. The RA will periodically contact the subject to make sure he/she is using the phone app and Withings watch and to answer any questions they may have about the app.
14. At week 12 the therapist will determine whether their subjects in Relief are eligible for an additional \$50 gift card based on the activities they have completed, and will distribute gift cards accordingly.
15. After the 12-week assessment, the patient in UC/RMH will receive an evaluation from a clinician.
16. All technology lent to patients will be returned to study staff.

RESEARCH ASSESSMENT

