The research assistant will describe the study, ask potential participants to sign consent, and administer a screening assessment to evaluate eligibility. Once this is confirmed, the research assistant will administer a baseline assessment. At this assessment, the research assistant will explain that follow-up assessments will be administered at 6, 9, and 12 weeks. The research assistant will also explain that the participants will be compensated \$25 for each completed assessment. The research assistant will then facilitate a referral to the data manager, who will identify the participant's group and notify [name], who will notify the appropriate social worker to schedule a meeting.

Inclusion Criteria:

1. 50 years or older
2. PHQ-9 score ≥ 10
3. Chronic pain (most days over the past 3 months)
4. Capacity to consent

Exclusion Criteria:

1. DSM-5 Axis 1 diagnoses other than depression and anxiety disorders (by SCID)
2. Montreal Cognitive Assessment (MoCA) < 24
3. Active suicidal ideation (MADRS item 10 ≥ 4)
4. Severe or life-threatening medical illness

*Note: Patients on psychotropic medications, opioids or benzodiazepines will be included if they do not meet DSM-5 criteria for opioid, anxiolytics or other substance abuse disorders (Human Subjects).

INTERVENTION

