Data will be collected by the study RA at baseline and at follow-up assessments. The RA will also be responsible for writing and presenting patient summaries to the PI. The clinician will complete updates on the progress of their therapy sessions. [name] manages the Relief database and weekly reporting.

Research records will be kept confidential to the extent permitted by law. Subjects will be assigned ID numbers by the Relief study team and all identifying information will be removed from records that are submitted to Weill Cornell Medicine for data analysis. Paper research records will be kept in locked file cabinets. When necessary for purposes of auditing, the Cornell IRB, NIMH, and all Federal oversight agencies will be provided to these files. Computers will be password protected and all staff participating in the study are trained in protecting human subjects in research. Data will be published in aggregate form without unique identifiers. No analyses will be published in which it is possible to identify individuals based on data.

SUSTAINABILITY

[name] will train three LCSWs in Relief (or more if needed). Training will consist of a one-day workshop with didactics, role-play and review of previously audiotaped sessions. After the workshop, the therapist will administer 6 Relief sessions to 2 pilot participants during the first four months. To be certified in Relief, therapists must achieve a score of greater than or equal to 4 (very good) out of 5 on the Relief Adherence Scale.

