**Aim 4: Preliminary Effectiveness:** We will use separate linear mixed models for primary and secondary outcomes measured at baseline, 6, 9 and 12 weeks with a subject-specific random intercept and slope and fixed effects for time, treatment, practice, therapist, treatment x time interaction. We will use model building and fitting strategies. In the final model, we will also estimate end of treatment improvements in outcome (from baseline) within each treatment group. As this is an underpowered developmental study, we will control false discovery rate using the Benjamini-Hochberg approach, and not the Family-Wise Error Rate, to adjust for multiple comparisons. Our primary goal will be to estimate effect sizes (or percentage reductions from baseline) with 95% CI and assess clinical significance. Using approaches of Initiative 2.1 (Methods Core), we will conduct exploratory joint analysis of primary and secondary longitudinal outcomes. We will also test between group differences in use of mobile technology measures described in 3b8 above and employing the time series approach of Initiative 2.1 (Methods Core). **Aim 5: Mediation:** For each mediator (MAIA, PANAS, secondary measures) we will use the cross-lagged panel model method to estimate the time-specific and treatment effect on outcomes related to the mediator. In exploratory analysis, we will estimate the indirect effect of longitudinal mediators (Initiative 2.1, Methods Core).

**Exploratory Aim:** We will repeat analyses of Aims 4 and 5 separately for each sex and provide sex-specific estimates of effectiveness and target engagement. We will compare the effect of Relief vs. RMH on quality of life (WHOQL-BREF), on opioid and benzodiazepine use (generalized linear mixed models), and suicidal ideation (MADRS item 10) as in Aim 4. To evaluate cost and potential savings, we will: a) compare the reimbursable and non-billable cost of the interventions, i.e. hours of administrative time, therapists' training, supervision vs. change in use of health care services (assessed by the CSI) by participants in Relief vs. RMH.

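### The Aim 4 model leaves the baseline arm difference free although patients are randomized after baseline; a common baseline mean would tighten the week-12 estimate at almost no cost, once the therapist term is recoded

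*SAP*

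**What the plan says.** SAP 3c, Aim 4: "We will use separate linear mixed models for primary and secondary outcomes measured at baseline, 6, 9 and 12 weeks". Each patient has a random intercept and slope, and the model has "fixed effects for time, treatment, practice, therapist, treatment x time interaction". The stated purpose is estimation: "Our primary goal will be to estimate effect sizes (or percentage reductions from baseline) with 95% CI". The same paragraph also asks for each arm's change from baseline to the end of treatment. It does not say whether time is linear or categorical.

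SAP 3c, Power, plans precision for the between-arm difference at week 12, with 40 patients in Relief and 20 in the comparison arm across 4 practices. It gives an 80% interval width of 0.66-0.75 and describes the simulated design as cluster randomized.

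Protocol, Research Assessment, puts baseline straight after eligibility: "Once this is confirmed, the research assistant will administer a baseline assessment". Only afterwards does the allocation step come: "The research assistant will then facilitate a referral to the data manager". Step 6 of the numbered procedures makes the patient the unit: "The data manager will randomize the patient to either Relief or UC/RMH". Step 9 says that the supervising therapist "will assign a therapist to the patient if randomized to Relief"; UC/RMH patients get none. Under Sustainability, three social workers are to be trained, or more if required.

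**The concern.** With baseline in the outcome vector and a treatment main effect, the fitted model has a free parameter for the arm difference at baseline. Randomization after baseline makes that parameter zero in expectation. Estimating it discards information that the baseline score carries about the week-12 difference. In a trial of 60 patients whose stated goal is effect sizes with intervals, that information is worth having.

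The usual remedy is to delete the treatment main effect. Here it fails. If UC/RMH is the no-therapist level, the therapist indicators add up to the Relief indicator. The treatment main effect is then not separately estimable, and when it is deleted the therapist indicators take over its role. If one therapist serves as the reference level instead, the fitted treatment effect is the effect for that therapist's patients only.

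**Working it through.** **Inputs from the documents.** 40 vs 20 patients, 4 practices, level-1 ICC 0.25-0.45, 80% width 0.66-0.75 (SAP, Power); visits at weeks 0, 6, 9, 12 (SAP, Aim 4); three therapists (Protocol, Sustainability).

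**Assumptions.** Level-1 ICC read as the within-patient correlation ρ; unit baseline SD; balanced practices; therapist caseloads 14/13/13; complete data and random intercept only, unless stated. Pairs below are ρ = 0.25 / 0.45.

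**1. The plan's own figure.** SE = √(1/40 + 1/20) = √0.075 = 0.274. The 80% width is 2 × 1.2816 × 0.274 = 0.70, inside 0.66-0.75. The exact endpoints cannot be reproduced, because the simulation's time coding and variance split are not given. A true cluster design effect with 15 patients per practice would give 0.702 × √(1 + 14 × 0.05) = 0.92 to 0.702 × √(1 + 14 × 0.10) = 1.09, so the stated width fits patient-level allocation.

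**2. Categorical time.**
- Free baseline: variance 0.075, SE 0.274 / 0.274.
- Common baseline: variance 0.075 × (1 − ρ²), SE 0.265 / 0.245.
- Excess: 1/√(1 − ρ²) − 1 = 3% / 12%.
- Equivalent patients: 60/(1 − ρ²) − 60 = 4 / 15.
- 80% width: 0.702 falls to 0.680 / 0.627.

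**3. Linear time.** Scale time to 0, 0.5, 0.75, 1: mean 0.5625, sum of squares about the mean 0.547. For a patient's fitted line:
- week-12 variance = ρ + 0.6(1 − ρ) = 0.70 / 0.78
- baseline variance = ρ + 0.829(1 − ρ) = 0.871 / 0.906
- covariance of the two = ρ − 0.2(1 − ρ) = 0.10 / 0.34

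The SEs follow:
- Free baseline: √(0.075 × 0.70) = 0.229; √(0.075 × 0.78) = 0.242.
- Common baseline: √(0.075 × (0.70 − 0.10²/0.871)) = 0.227; √(0.075 × (0.78 − 0.34²/0.906)) = 0.221.
- Excess: 1% / 9%, or about 1 / 12 patients.

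**4. Random slopes.** The documents give no slope variance. With an assumed week-12 slope variance of 0-0.2 and intercept-slope correlation of −0.3 to +0.3, the excess over both values of ρ is about 2-13% (categorical) or 0-10% (linear).

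**5. Estimated variances and dropout.** Random intercept and slope fitted by REML with practice and therapist (categorical time, 600 simulated trials in each of 8 settings) give a mean-SE excess of 2-4% / 8-12%. The 95% intervals cover 95-97% with and without the constraint. With an assumed 20% dropout by week 12 the excess is 2.6% / 9.8%; with 30%, 2.3% / 8.7%.

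**6. Therapist term, categorical time.** Columns: intercept 1, time 3, treatment 1, interaction 3, practice 3, therapist 3, total 14; rank 13.
- Treatment main effect deleted: 13 columns, rank 13, same column space. The therapist-averaged week-12 SE stays at 0.274 / 0.274.
- Common baseline, therapist centred within Relief and post-baseline only: 0.265 / 0.245.
- Effect for one reference therapist (caseload 14): 0.309 / 0.320, which is 13% / 17% above 0.274.

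With linear time, a full set of uncentred post-baseline therapist indicators gives 0.235 / 0.224. At ρ = 0.25 that is worse than the planned 0.229, so the centring matters.

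**7. Baseline as covariate, weeks 6-12 only.** With linear time the SE is 0.247 / 0.230, against 0.229 / 0.242 as planned: 8% higher / 5% lower.

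**The case against.** The strongest reply is that nothing is broken. The model is an accepted choice, its intervals cover, the planned width is met, and the SAP itself calls the study underpowered and developmental. At ρ = 0.25 the gain is 3% or 1%. All of that stands, and it limits the point to an optional improvement.

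The size also depends on inputs that the documents do not give. Other ways of splitting the practice variance give 1.4-15.5% (categorical) or 0-13.1% (linear), and larger slope variances bring the categorical figure down to 0.8%. That too stands.

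The SAP opens by promising to check baseline balance and adjust, and Aim 4 allows for model building. Neither names the baseline outcome score or constrains the arms at baseline, and the obvious model-building step, deleting the treatment term, has no effect while therapist indicators remain.

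A baseline-covariate model might look simpler. It loses precision at ρ = 0.25 if time is linear, and it does not directly give the within-arm changes that Aim 4 requires. The random slope hints at linear time without settling it.

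A reader might infer more than the documents support:
- *The estimate is biased, or the precision target is missed.* Neither is so (steps 1 and 5).
- *The loss is 17-41%.* Those figures (26% / 17% categorical, 41% / 24% linear) apply only if treatment-by-time is reported as the effect. The Power paragraph plans for the week-12 difference.
- *The treatment effect cannot be estimated.* Only the separate main effect is lost; the therapist-averaged week-12 difference remains estimable.
- *The reference-therapist problem is certain.* It arises under one coding, and the SAP specifies none.

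**Conclusion.** The point holds as a free improvement. At the same time coding, a common baseline mean gains precision or at worst breaks even. The planned model's week-12 SE is about 3% / 12% larger (categorical) or 1% / 9% larger (linear) at ρ = 0.25 / 0.45, and about 2-13% or 0-10% over the assumed slope variances. At the low end this is negligible; at the high end it is worth 12 to 15 patients on 60, from a score that is already collected. Dropout reduces it.

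These sizes rest on reading the level-1 ICC as the within-patient correlation, on assumed slope variances, and on patient-level allocation after baseline. The therapist aliasing does not depend on the ICC. It follows from assigning therapists in one arm only and entering them as fixed effects at every visit.

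**What to change.** In SAP 3c, Aim 4:

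1. Keep the four-visit mixed model and state whichever time coding was intended.
2. Constrain the two arms to a common baseline mean: no treatment main effect, and arms differing only after baseline.
3. Enter therapist as indicators centred within Relief (indicator minus that therapist's share of Relief patients, zero in UC/RMH) that act only after baseline, or remove it. Without this, step 2 has no effect when time is categorical.
4. Name the week-12 between-arm difference, averaged over therapists, as the effect estimate, in line with the Power paragraph.

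The within-arm changes from baseline remain available from the same model. Modelling weeks 6-12 with the baseline score as covariate is an alternative only if time is categorical, and the within-arm changes would then need a separate calculation.

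Reconcile the cluster-randomized wording in Power with patient-level randomization in Protocol step 6. Confirm that every patient's baseline precedes allocation, because the constraint rests on that.

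The cost is SAP wording and a small change of model code. No new data or visits are needed.

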**NCT 03265210**

**10/14/2016**

**3c. STATISTICAL ANALYSIS PLAN:** We will examine the distribution and outliers for each variable, and use transformations or bootstrapping if needed. We will test whether baseline demographic and clinical variables are balanced between groups and practices, and adjust in analyses (based on intention to treat principle).

**Aim 3: Reach, Feasibility, Acceptability of Relief and RMH:** We will calculate estimates and 95% CI of the following measures for all subjects and for each sex separately: 1) Reach: Proportions screened, and met study criteria for both conditions. 2) Feasibility: Proportions of patients who initiate Relief and proportion of RMH patients who contact mental health care services; research procedures (timely referrals, assessments) in both conditions; Relief session completion rates and smartphone use. 3) Acceptability to patients: CSQ at baseline, 6, 9, and 12 weeks will be analyzed as in Aim 4. Relief Benchmark tests: >75% session attendance rate, >70% smartphone ratings, and CSQ score  $\geq 3$  (out of 4) will be performed using one-sample z-tests of proportions. We will evaluate clinician and practice staff satisfaction every 6 months.

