**Power:** Consistent with the R34 mechanism, we did not perform power analysis. Instead, we calculated the width of the confidence interval (CI) for estimated effectiveness. We simulated 1000 datasets following a 2-level cluster randomized longitudinal design (N=40 in Relief vs 20 in RMH in 4 practices), a range of intra-class correlations (ICC) and estimated the width of CI for treatment difference (Cohen's d) at week 12 using linear mixed effects regression model. For 80% confidence of the CI, the estimated CI width will be 0.66-0.75. The range of CI width is based on a range of ICCs for level 1 (0.25-0.45) and 2 level (0.05-0.10) clusters. The estimated CI width is consistent with reported CI widths of effectiveness estimates obtained in meta-analyses of RCTs comparing CBT with control conditions in depression.

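### Aim 4 enters treatment and therapist as fixed effects, but only Relief patients are assigned a study therapist, so a week-12 level difference read from the treatment terms depends on the reference therapist

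*SAP*

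**What the plan says.** SAP section 3c, Aim 4, plans separate linear mixed models for outcomes at baseline and weeks 6, 9 and 12. Each has a random intercept and slope per patient and "fixed effects for time, treatment, practice, therapist, treatment x time interaction". There is no therapist x time term, and therapist is not random. The section adds "We will use model building and fitting strategies", and then: "Our primary goal will be to estimate effect sizes (or percentage reductions from baseline) with 95% CI". It also plans within-arm improvement from baseline.

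What the effect size refers to has to be read from two other places:

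- The Power paragraph of section 3c says the authors "estimated the width of CI for treatment difference (Cohen's d) at week 12 using linear mixed effects regression model", which names a week-12 difference.
- Item 4 of the protocol's Study Aims says Relief participants "will have greater (effect size) and clinically significant reductions in depression, pain-related disability", which is about change.

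On therapists, step 9 of the protocol's procedure list says that the supervising therapist "will assign a therapist to the patient if randomized to Relief". Under Intervention, UC/RMH care is left to the practices and only recorded. The Sustainability section plans three Relief therapists, with room for more. Neither document gives a therapist code for UC/RMH patients, a reference therapist, a nesting or a constraint.

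**The concern.** If only Relief patients have a therapist, knowing the therapist means knowing the arm. Treatment and a full set of therapist indicators cannot then both be separately identified. Software will drop one column without comment, and the column dropped decides what the treatment coefficient means. If the analyst adds the treatment main effect to 12 weeks of the treatment x time slope to get the week-12 difference named under Power, the value and its standard error depend partly on a coding default.

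Estimating effect sizes with intervals is Aim 4's stated primary goal. The model is also reused: "CSQ at baseline, 6, 9, and 12 weeks will be analyzed as in Aim 4", and the Exploratory Aim applies it by sex and to quality of life and suicidal ideation. One clarification would cover all of these.

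**Working it through.** **1. The plan's own precision figure.** SAP Power gives 40 vs 20 patients, 80% confidence and a CI width of 0.66-0.75 for Cohen's d at week 12. The simple formula is 2 x 1.2816 x sqrt(1/40 + 1/20) = 2 x 1.2816 x 0.2739 = 0.702, inside the stated range. Removing a practice ICC of 0.05 or 0.10 gives 0.702 x sqrt(0.95) = 0.684 or 0.702 x sqrt(0.90) = 0.666. The upper end of 0.75 cannot be confirmed, because the simulation settings are not given. Nothing below depends on it.

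**2. Rank.** Let T = 1 for Relief, and let H_k = 1 if the patient has therapist k (all zero in UC/RMH). Then H_1 + H_2 + H_3 = T for every patient.

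- Linear time: intercept, time, treatment and treatment x time (4), practice (3) and therapist (3) make 10 columns, with rank 9.
- Categorical time: 14 columns, rank 13.
- One therapist per practice: also one short (9 columns, rank 8, time terms left out).

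This step needs no assumption about variances or caseloads.

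**3. What is affected.** Write the Relief-specific part of the mean as d + g x time + h_k. Adding a constant to d and subtracting it from every h_k leaves the fit unchanged. With therapist r as reference, the treatment coefficient estimates d + h_r, so:

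- d + h_r and d + h_r + 12g depend on r.
- g does not, because the model has no therapist x time term. The between-arm difference in change and both within-arm changes are therefore safe.
- d + 12g + sum(w_k h_k), with weights w_k adding to 1, is the same under any coding.

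**4. Size when therapists do not differ.** Generalised least squares: Var(b) = (X'V^-1 X)^-1, with V = Z diag(ICC, s^2) Z' + (1 - ICC) I at weeks 0, 6, 9 and 12.

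- From the SAP: 40/20 patients, 4 practices, level 1 ICC 0.25 or 0.45.
- Assumed: linear time; baseline variance 1; patient slope SD s of 0.3, 0.5 or 0.8 over 12 weeks; zero intercept-slope covariance; 10 Relief and 5 UC/RMH patients per practice; the caseloads below.

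Without therapist, the week-12 SE is 0.243-0.326, a 95% half-width of 0.48-0.64 baseline SD (1.96 x SE). The departure is the mean absolute gap between one reference-coded coefficient and the equal-weight therapist average, sqrt(2/pi) x SD of the gap.

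| Relief caseloads | SE ratio, reference coding / no therapist | Mean departure (SD) |
|---|---|---|
| 14/13/13 | 1.126-1.221 | 0.121-0.152 |
| 4 x 10 | 1.197-1.308 | 0.150-0.185 |
| 5 x 8 | 1.254-1.393 | 0.172-0.213 |
| 20/10/10 | 1.069-1.308 | 0.115-0.167 |
| 3 therapists in separate practices | 1.196-1.765 | 0.199-0.288 |

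At 14/13/13 the reference-coded half-width is 0.56-0.74, and the departure is 22-28% of the half-width without therapist. The treatment x time SE ratio is 1.0000.

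**5. Size when therapists do differ.** Assume 14/13/13, a treatment effect of -0.50 at week 12, and therapist effects of -0.3, 0 and +0.3 SD, so that the therapist-specific week-12 differences are -0.80, -0.50 and -0.20.

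- Effects constant over all visits, baseline included: the reference-coded values are -0.80, -0.50 and -0.20, a full shift to the reference therapist.
- Effects growing linearly from zero at baseline: -0.61 to -0.66, -0.50, and -0.35 to -0.40. The share of the departure captured is (0.61 - 0.50)/0.30 = 0.37 to (0.66 - 0.50)/0.30 = 0.53 for the first therapist, and (0.50 - 0.40)/0.30 = 0.33 to (0.50 - 0.35)/0.30 = 0.50 for the third.

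**The case against.** The strongest reply is that Aim 4 is mostly about change. The protocol hypothesises reductions, and the SAP has a treatment x time term, percentage reductions from baseline and within-arm improvement. None of these is touched. Harm requires an analyst to report a week-12 level difference, build it from the raw treatment coefficients, and not average over therapists. Only the Power paragraph points to the first of these, and it describes a precision simulation. This stands, and it is why the point is minor. It does not remove the point: the SAP names a week-12 difference and does not say which quantity supplies the effect sizes.

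The SAP text is also a section of a longer document. A provider seeing patients in both arms, or a therapist code for UC/RMH defined elsewhere, would remove the deficiency. The visible text gives neither, so the point is conditional on therapist having levels only in Relief.

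Four stronger readings are tempting but unsupported:

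- *The treatment effect cannot be estimated.* Only the main effect, and quantities built on it without averaging, are unidentified.
- *The coefficient describes one therapist.* This is exact only if therapists' patients differ equally at every visit, including before therapy starts. If effects build up from baseline, about a third to a half of the departure comes through.
- *The redundant term will be chosen after the outcomes are seen.* The SAP does not say how model building will treat it, but the redundancy follows from the design and can be settled before any outcome is observed.
- *Difference in change must be the effect size.* That is a choice of estimand; a therapist-averaged level difference is equally valid.

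**Conclusion.** The point holds in limited form, with minor severity. With therapist levels in Relief only, the listed fixed effects are one rank short, and a week-12 level difference read from the treatment terms is not identified until a coding is chosen. The rank result is algebra. The sizes (SE 13-22% wider and a mean departure of 0.12-0.15 SD at 14/13/13) rest on the assumed caseloads, slope SDs, zero covariance, linear time and even spread over practices; the SAP supplies only the arm sizes, number of practices and ICC range. With more therapists, or therapists confined to separate practices, both sizes can be larger. If therapists truly differ, the estimate is pulled toward the reference therapist by an amount that depends on how the differences develop over time. The comparison of change that tests the protocol's hypothesis stands as planned.

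**What to change.** In Aim 4:

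1. Enter therapist nested within Relief, coded 0 for UC/RMH, with a sum-to-zero constraint.
2. State that any week-12 level difference is averaged over Relief therapists, weighted by patients treated. A plain sum-to-zero constraint makes the treatment terms an equal-weight average, so the patient-weighted version should be written as an explicit contrast.
3. State whether the reported effect size is that averaged level difference or the treatment x time difference in change. Either is valid.

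The cost is a few sentences. Precision for treatment x time is unchanged. Weighting by patients treated costs 0.0% in SE for the level difference in every layout tried. Equal weights would cost 0.0% at 14/13/13, 0.8-1.3% at 20/10/10, and 2.4-3.8% with three therapists in separate practices. The same wording serves the CSQ, sex-specific, quality-of-life and suicidal-ideation analyses. A random therapist effect in the Relief arm only is an alternative, but is not needed to correct this.
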